7. STUDY DESIGN

The *UK Chiari 1 Study* will be a prospective, multi-centre cohort study and will be complete after three years. The study is purely observational and will not alter patient care in any way.

The study will collect both patient- or parent- reported (hereafter referred to as patient-reported) and surgeon-reported data. The study design allows for remote, online data collection and therefore does not require further visits to the hospital or any other facility. Participants will be required to provide patient-reported data at baseline and 12-months following baseline. Additionally, if the patient undergoes a decompressive surgery, then they will be asked to provide patient-reported data 12-months after their surgery. The maximum duration of follow up following baseline, therefore, will be 12-months for patients who do not undergo decompressive surgery and 24-months for patients who do undergo decompressive surgery.

8. PARTICIPANT IDENTIFICATION

8.1. Study Participants

Participants will be patients with a new diagnosis of CM1 presenting to neurosurgical clinic for the first time. Participants will be eligible from the age of 0 days and there is no upper age limit.

8.2. Inclusion Criteria

The participant may enter the study if both of the following apply:

- Patients of 0 days of age and above who are referred to a neurosurgeon with CM1. A diagnostic threshold based on millimetres of herniation below the foramen magnum is not specified (as there is no evidence-based threshold and may introduce bias and inappropriately eliminate cases). Further analysis of clinical features and outcomes with the severity of herniation may be conducted.
- Patients seen for the first time in a neurosurgical outpatient clinic within the study recruitment period.

8.3. Exclusion Criteria

The participant may not enter the study if ANY of the following apply:

- Patients considered to have an alternative Chiari malformation (type 2, 3 or 4).
- Patients with a history of spinal dysraphism.
- Patients who have already undergone neurosurgical intervention for Chiari malformation or an alternate neurological diagnosis.

9. PROTOCOL PROCEDURES

Procedures	Timepoint
Recruitment	Baseline
Outcome data collection [all patients]	12-months following baseline
Outcome data collection after decompressive surgery [sub-set of patients undergoing decompressive surgery]	12-months following decompressive surgery

9.1. Recruitment

The study will follow the BNTRC model for multi-centre, trainee-led collaboration (Chari *et al.*, 2018) and each participating UK neurosurgical unit (NSU) will be required to commit both a Consultant Principal investigator (PI) and a Trainee co-PI. Whilst as many possible interested consultants are welcome to participate as collaborator, we will be particularly interested in the input of consultant neurosurgeons frequently seeing patients with CM1 to participate in order to detect as many patients as possible. Considering the length of the study, trainee investigators may have to handover to trainee co-PI role to another trainee during the study course, but this will not interfere with the study design. All UK NSUs will be invited to participate.

Participating sites may commence their own 12-month recruitment period with a start date between 8th October 2020 to 7th April 2021.

9.2. Screening and Eligibility Assessment

Patients will be identified by participating neurosurgical consultants and trainees. The neurosurgical team will ask permission for the patient to be contacted by the study team (i.e. the researchers working on the study at that particular hospital / neurosurgical unit) via telephone.

Eligible patients may be enrolled at any point, but in order to be included in the primary outcome analysis (patient-reported), patients must be enrolled within 45 days of the first clinic appointment. Those enrolled after 45 days will have only their record-based data included in the secondary analyses.

Patients must satisfy all of the inclusion and exclusion criteria of the protocol. There will be no exceptions.

Neurosurgical units (NSU) that join the study after the overall study has commenced will be able to retrospectively recruit patients from the start of the overall study start date (8th October 2020), provided that the patients were seen in their first neurosurgical clinic within the last 45-days. Again, the neurosurgical team will make the first contact with the patient and ask the patient's permission for them to be contacted by the study team. This will be documented in the patient's notes. The study team will then contact the patient and continue with the consent process.

9.3. Informed Consent

After identification, patients will be contacted via telephone by a member of the study team who will explain the details of the study, its aims and what it involves for the participant. The person who obtained the consent must be suitably qualified and experienced and have been authorised to do so by the Chief Investigator (CI). The study will be explained and if the patient agrees then the patient will be sent an email that contains:

- a PDF version of the participant information sheet
- a hyperlink to the digital consent form

The digital consent form will be a submission form linked to our REDCap study database. Patients will explicitly be consented for their email address to be stored on the database. Patients will draw an electronic signature, type their name and type the date on the electronic consent form. A copy of the signed informed consent will be sent via email to the patient, a copy will be saved to the local study site and a copy will be saved at the Sponsor site.

If patients prefer or if they do not have an email address, they can choose to have these documents sent to them via post (including two copies of the consent form (both signed by the study team member taking consent) and participant information sheet). Patients will be given an addressed, stamped envelope so that they sign and return one copy of the consent form back to their local neurosurgical unit. The returned consent form will be filed in a local NSU filing system. Data collection would not start before the local NSU has received the signed consent form.

Patients will be given sufficient time to consider the study and patients will have the contact details of their local NSU investigators so that they may ask questions. Patients must be told that the study is completely voluntary. Patients may withdraw from the study at any time for any reason without prejudice to future care, without affecting their legal rights, and with no obligation to give the reason for withdrawal. If a patient withdraws, identifiable data or tissue already collected with consent would be retained and used in the study. No further data would be collected or any other research procedures carried out on or in relation to the participant.

The parents or legal guardians will consent for children (<16 years) approached for the study and the parents' contact details will be used. If a child turns 16 years of age during the study period, then the patient will be reconsented to remain in the study. For patients who lose capacity during the process of the study will not be contacted again, but the previous information collected (as per their valid consent) will be retained.

The BNTRC Chiari 1 Study is currently limited to 12-month follow up. At the time of consent, an additional option will be for patients to consent to being contacted for future studies. A potential future study will be to collect outcome data at five and/or ten years, but these are considered separate and are not within the current study protocol.

Patients will be given the additional option on the consent form to be contacted following the completion of the study for the synopsis of the overall study results to be emailed to the email address they provided.

9.4. Blinding and code-breaking

This study will not use a blinding procedure.

9.5. Description of study intervention(s), comparators and study procedures (clinical)

This study is only observational.

9.5.1. Description of study procedure(s)

Data collection will have two sources:

The first source is **patient-reported data** and will be acquired at baseline, at 12-months. Additionally, if the patient undergoes decompressive surgery, patients will be asked to complete a survey 12-months after their operation. This patient-reported model of data collection has been piloted and shown to be feasible by the Understanding Cauda Equina Study (Woodfield et al., 2018). After completion of the consent form, patients will have a secure survey sent to them via our online database system called REDCap (explained section 12.3). Once patients have been added to the REDCap system, they will automatically be sent an email invitation when each follow up phase is due. If patients do not want to use the online-based system, then they will be given the option to give their data via post or telephone. If patients do not respond to the initial automated email invitation, local collaborators or the study steering group will contact them via phone to ensure that they have received the invitation.

For children enrolled in the study, it is the parents who will complete the survey, not the child.

The second source is **surgeon-reported data** and will require observational data collection from patient notes, imaging and surgical logs. This data input is performed by the local collaborating study team. We list the full list of data fields in Appendix 3.

9.6. Baseline Assessments

Patient-reported data at baseline will consist of an online questionnaire, including the baseline HRQoL assessment. For a patient's baseline HRQoL to be included in the analysis, the questionnaire must have been completed by 45-days after being seen in the neurosurgical clinic.

Surgeon-reported data at baseline will be by review of clinical records by the study team at the participating NSU.

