9.7. Subsequent Assessments

All patients will be followed up at 12-months following first neurosurgical clinic attendance. Patients will be sent an email with a link to the online questionnaire. Either the local study team or steering committee may phone the patient if there is no response to the online questionnaire after seven days.

Surgeon-reported data based on clinical records will also be inputted to the database at the 12-month mark. At the time of this data review, the local investigators will identify a sub-group of the patients who have undergone decompressive surgery since enrolment in the study. For patients who have undergone decompressive surgery, an additional 12-month follow up questionnaire shall be scheduled. Similarly, this sub-group of patients will be sent an email with a link to their questionnaire 12-months after their

operation and the study team or steering group may follow up with a phone call, if necessary, after seven days.

For each follow up timepoint, patient-reported data (i.e. questionnaires) must be completed within 45-days from the target date to be included in the analysis).

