11.2. Description of the Statistical Methods

For the primary outcome, the baseline and 12-month HRQoL assessments will be used for analysis. For all patients, comparison will be made between baseline and 12-months, but both will also be compared against the UK normative datasets.

For the secondary outcome pertaining to the sub-group undergoing decompressive surgery, HRQoL data will be similarly be compared to baseline and to UK normative datasets. Further comparisons of outcome data will be made between specific surgical techniques used, baseline symptoms and radiological findings.

Descriptive statistics will be used to report the data from the exploratory objective, regarding referral pathways, investigations and management strategies for CM1 in UK neurosurgical practice.

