21. APPENDIX A: STUDY FLOW CHART

22. APPENDIX B: SCHEDULE OF STUDY PROCEDURES

Procedures	Day 0	Day 0*	12-months*	12-months after date of decompressive surgery*
Baseline	x			
First neurosurgical clinic	x			
Identified as eligible	x			
Approached for study		x		
Consented for study		x		
12-month patient-reported data			x	
12-month surgeon-reported data			x	
Additional 12-month patient-reported data (for decompressive surgery group)				x
Additional 12-month surgeon-reported data (for decompressive surgery group)				X
*45 days are allowed for patients to complete the questionnaire.				

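### A baseline questionnaire counts if it is completed by day 45 after clinic, even when the patient enrolled, had CM1 surgery and only then filled it in

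*Protocol*

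**What the plan says.** **Baseline timing.** Under Protocol section 9.6, a baseline score is analysed only if "the questionnaire must have been completed by 45-days after being seen in the neurosurgical clinic". The footnote to the schedule in Appendix B gives the same allowance: "45 days are allowed for patients to complete the questionnaire". Neither mentions the date of an operation.

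**Enrolment timing.** For the primary analysis, section 9.2 says "patients must be enrolled within 45 days of the first clinic appointment". The questionnaire follows consent (section 9.5.1): "After completion of the consent form, patients will have a secure survey sent to them via our online database system called REDCap".

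**Surgery before entry.** Section 8.3 excludes "Patients who have already undergone neurosurgical intervention for Chiari malformation or an alternate neurological diagnosis". Section 9.2 allows no exceptions to the eligibility criteria.

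**Surgery after entry.** Section 9.7 has local investigators, at the 12-month record review, "identify a sub-group of the patients who have undergone decompressive surgery since enrolment in the study".

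**Use of the baseline.** Section 11.2 sets out the primary analysis: "For all patients, comparison will be made between baseline and 12-months". For the decompression sub-group it adds that "HRQoL data will be similarly be compared to baseline and to UK normative datasets".

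Section 11.1 states that no separate statistical analysis plan is in use, so these sections hold all the rules on the point.

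**The concern.** A baseline for a before-and-after comparison has to be measured before the event whose effect is being described. The protocol anchors the baseline to the clinic date alone. Surgery can fall inside the 45-day allowance, and nothing sets aside a form completed after it.

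Secondary objective 1 is the most exposed, because its whole contrast is 12 months after decompression against baseline. The same score also enters the primary change, the comparisons between surgical techniques in section 11.2, and secondary objective 4, which relates tonsillar herniation to baseline quality of life. Only patients operated on within 45 days of clinic can be affected, so any error falls on a particular group and is not spread over the cohort. A pre-operative score that was missed cannot be recovered later. Deciding which baselines count once the data are in would be a post hoc choice.

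**Working it through.** **1. What the rules admit.** Count days from the first clinic (day 0). The example days are illustrative.

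| Sequence | Outcome under the written rules |
|---|---|
| Consent day 7, form day 10, surgery day 14 | Valid pre-operative baseline |
| Consent day 7, surgery day 14, form day 40 | Accepted: enrolled by day 45, no surgery before entry, form by day 45. The score is taken 40 − 14 = 26 days after surgery |
| Surgery day 14, consent day 20, form day 40 | Excluded if section 8.3 is applied at entry. Appendix B lists the eligibility step under Day 0, so this case is not fully clear |
| Consent day 7, surgery day 14, form day 50 | Rejected by the 45-day limit |

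The second row is the gap. If the operation was a decompression, section 9.7 places that patient in the surgical sub-group, because the surgery came after enrolment. No section checks the operation date against the questionnaire date.

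**2. Inputs for a size.** The documents give no interval from clinic to surgery, no proportion operated on and no early post-operative shift in quality of life. The only nearby figures are the recruitment projection in section 11.3. It reproduces: (11 + 4) × 12 × 0.50 = 90 per year in two units, and 90 ÷ 2 × 12 = 540, which exceeds 500. It carries no information on this point. Everything below is therefore illustrative.

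**3. Relative effect on secondary objective 1.** Let D be the true mean change in operated patients, f the share of them with a post-operative baseline, and s the part of the eventual change already present in that baseline. The observed mean change is

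(1 − f) × D + f × (1 − s) × D = D × (1 − f × s).

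| f | s = −0.5 (early drop) | s = 0.5 (partial early relief) | s = 1 (full early relief) |
|---|---|---|---|
| 5% | 1.025 | 0.975 | 0.95 |
| 10% | 1.05 | 0.95 | 0.90 |
| 20% | 1.10 | 0.90 | 0.80 |
| 30% | 1.15 | 0.85 | 0.70 |

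Factors above 1 overstate the change and factors below 1 understate it.

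**4. The same in points.** The size of the error is f × shift. With an assumed shift of 10 points: 0.05 × 10 = 0.5; 0.10 × 10 = 1.0; 0.20 × 10 = 2.0. A temporary drop makes the error an overstatement of improvement, and early relief makes it an understatement.

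**5. Primary analysis.** This covers all patients, so the error is multiplied by the proportion operated on. If that were one half (assumed), 0.5 × 0.5 = 0.25 and 0.5 × 2.0 = 1.0, so the range would be 0.25 to 1.0 points in either direction. Section 11.4 analyses adults and children separately, so these proportions would apply within each group.

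**The case against.** The best defence is that the protocol already closes most of the window. Section 8.3 bars anyone operated on before entry, section 9.2 permits no exceptions, and section 9.7 counts only surgery since enrolment. The survey goes out after consent, and non-responders are telephoned. The clear exposure is therefore the delay between consent and completion, not the full 45 days. It also needs an operation soon after a first outpatient visit, which may be rare. The operation date is needed to schedule the post-operative questionnaire, so an analyst could probably identify the affected forms.

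Most of this stands, and it limits the point. A reader might infer that any patient operated on within 45 days of clinic can supply a post-operative baseline. Section 8.3, read as a rule on entry, does not support that. Some doubt remains about surgery between clinic and consent, because of where Appendix B places the eligibility step.

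The defence does not reach surgery after enrolment. Being able to identify the affected forms is also not a rule for handling them. Late completion is foreseeable: postal consent delays the start of data collection (section 9.3), enrolment may itself come late in the 45 days, and section 11.7 allows a missing questionnaire to be chased for up to 45 days.

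**Conclusion.** The point holds for one defined route: enrolment, then CM1 surgery, then a baseline form completed by day 45. As written, such a form is analysed as a baseline, and no other rule removes it. That conclusion rests on the text alone.

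The size is unknown and may be small. The illustrative 0.5 to 2.0 points in operated patients depends on an assumed 5% to 20% affected and an assumed 10-point shift. The figure for the primary analysis is smaller in proportion to the share operated on.

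Two stronger readings are tempting and not supported. One is that the benefit of decompression will be overstated; the direction depends on whether early recovery lowers or raises the score, and the documents say nothing on this. The other is that the affected patients are the most severe; nothing in the protocol links early surgery to severity.

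This is a moderate weakness. It does not invalidate the design, but it should be settled before the change analyses are run.

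**What to change.** - **Section 9.6:** require the baseline questionnaire to be completed within 45 days of the first clinic and before any surgery for CM1. Any CM1 surgery should be named, not only decompression, because other operations affect the primary change in the same way.
- **Section 11.2:** treat a questionnaire completed on or after the operation date as a missing baseline in the change analyses. Report how many there are, and show a sensitivity analysis that includes them.
- **Section 8.3 or Appendix B:** state that the prior-intervention exclusion is applied at consent, so that surgery between clinic and consent is clearly covered.

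The cost is a few sentences. Patient care does not change. A few early-operated patients drop out of the main change analyses, which loses a little precision and makes the surgical sub-group slightly less complete. The reported count and the sensitivity analysis let readers judge whether that matters.

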9.7. Subsequent Assessments

All patients will be followed up at 12-months following first neurosurgical clinic attendance. Patients will be sent an email with a link to the online questionnaire. Either the local study team or steering committee may phone the patient if there is no response to the online questionnaire after seven days.

Surgeon-reported data based on clinical records will also be inputted to the database at the 12-month mark. At the time of this data review, the local investigators will identify a sub-group of the patients who have undergone decompressive surgery since enrolment in the study. For patients who have undergone decompressive surgery, an additional 12-month follow up questionnaire shall be scheduled. Similarly, this sub-group of patients will be sent an email with a link to their questionnaire 12-months after their

operation and the study team or steering group may follow up with a phone call, if necessary, after seven days.

For each follow up timepoint, patient-reported data (i.e. questionnaires) must be completed within 45-days from the target date to be included in the analysis).

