2. LAY SUMMARY

Background

Chiari 1 malformation (CM1) is a structural abnormality of the hindbrain characterised by herniation of the cerebellar tonsils through the foramen magnum. The investigation and management of CM1 remains contentious since there are currently no UK guidelines for clinicians. Practice varies widely between neurosurgical units and individual surgeons, but there is no robust evidence to bring consensus to the selection of surgical candidates or to the specific surgical technique for CM1. We therefore propose a collaborative, prospective, multi-centre study on the investigation, management and outcome of CM1 in the UK.

Objectives

Our primary objective is to determine the patient- or parent-reported, health-related quality of life (HRQoL) in patients with a new diagnosis of CM1 managed either conservatively or surgically at 12 months follow up. This will be measured using the 36-Item Short Form Health Survey (SF-36; UK version) in adults (16 years and above) and the age-appropriate parent-reported Pediatric Quality of Life Inventory™ (PedsQL™ ; UK version) in children (2 to 15 years). We also aim to i) assess the scope and variation of contemporary investigations and neurosurgical management for CM1 in the UK; ii) determine factors that are predictive of postoperative outcome; iii) to examine the outcomes of varying surgical strategies (including HRQoL 12-months following decompressive surgery); and iv) to investigate the natural history of patients managed conservatively.

Methods

The UK Chiari 1 Study will be a prospective, multicentre and observational study that will follow the British Neurosurgical Trainee Research Collaborative (BNTRC) model of collaborative research. Patients will be recruited after attending their first neurosurgical clinic. Afterwards data are collected from all patients undergoing decompressive surgery, other surgery or being treated conservatively for CM1 in participating UK neurosurgical units. Data will be both patient- or parent-reported (via digital questionnaires) and surgeon-reported (via digital questionnaires). Each participating site will complete the study within three years.

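### Section 9.7 finds decompression patients by surgery since enrolment, while the study clock starts at first clinic and the prior-surgery exclusion in Section 8.3 carries no date

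*Protocol*

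**What the plan says.** Section 9.7 (Subsequent Assessments) sets the follow-up clock: "All patients will be followed up at 12-months following first neurosurgical clinic attendance". In the same section, the step that finds surgical patients at the 12-month record review uses another clock: "the local investigators will identify a sub-group of the patients who have undergone decompressive surgery since enrolment in the study". The next sentence schedules the extra questionnaire for patients who have had decompression and does not mention enrolment.

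Section 9.2 separates enrolment from clinic. For the primary analysis, "patients must be enrolled within 45 days of the first clinic appointment". Later enrolment is allowed: "Those enrolled after 45 days will have only their record-based data included in the secondary analyses". Appendix B puts baseline, first clinic and identification of eligibility in one Day 0 column, and approach and consent in a second, asterisked one.

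Section 8.3 excludes "Patients who have already undergone neurosurgical intervention for Chiari malformation or an alternate neurological diagnosis". It gives no date at which this is judged, and Section 9.2 allows no exceptions to the criteria.

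For the baseline score, Section 9.6 asks only that "the questionnaire must have been completed by 45-days after being seen in the neurosurgical clinic". It does not ask that the questionnaire precede surgery.

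Section 11.1 states that no separate SAP is in use, so the protocol text is the operative definition.

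**The concern.** The surgical sub-group supports secondary objective 1 (HRQoL 12 months after decompression) and objective 2 (complications and re-operation). If sites apply Section 9.7 as worded, a patient counts as surgical only if still unoperated at enrolment. Those at risk of being missed are the patients operated on soonest after clinic. They may differ from the rest, for example in urgency, although the protocol has no data on this.

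The order of events is foreseeable. Consent is taken by telephone after clinic and then by email or post (Section 9.3), and late-joining units may recruit patients seen in the previous 45 days (Section 9.2). Many local teams will carry out the record review, so the same kind of patient could be classified differently from one unit to another.

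A linked problem concerns the baseline score. A patient decompressed soon after clinic can return a post-operative questionnaire inside the 45-day window and have it accepted as baseline. The change score then no longer measures change from the pre-operative state.

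**Working it through.** **1. The plan's own figures.** Section 11.3 projects recruitment only: (11 + 4) × 12 × 0.5 = 90 a year in two units, and 90/2 × 12 = 540 in 12 units, which agrees with the stated figure of more than 500. These reproduce, and the point does not depend on them. The protocol gives no operation rate, waiting time or enrolment delay.

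**2. Time origins side by side.**

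| Place | Origin or limit |
|---|---|
| 9.7, follow-up | first clinic |
| Appendix B, baseline and eligibility | first clinic (Day 0) |
| 9.2, enrolment | up to 45 days after clinic, or later for record-based data |
| 9.7, search for surgical patients | enrolment |
| Section 6 objectives, Section 7, 9.5.1 | any decompression, no enrolment limit |
| 8.3, prior intervention | no date |

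**3. Two test patients.** A: clinic day 0, enrolled day 5, decompressed day 30. A is found by the search. B: clinic day 0, unoperated and eligible, decompressed day 20, enrolled day 35. B's status depends on how Section 8.3 is read:

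- *Judged at first clinic:* B may enter. The literal search finds no decompression after enrolment, so B may get no post-operative questionnaire or record review and may be unclassified or misclassified.
- *Judged at enrolment:* B is barred. Section 9.7 then drops nobody, because every decompression in the cohort follows enrolment, but the cohort has lost a patient who qualified at clinic.

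The two consequences are alternatives and do not add up.

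**4. Illustrative size (assumed timings).** Let S be days from clinic to surgery, uniform on 0-365, and E days from clinic to enrolment. The share of first-year operations that precede enrolment is P(S < E) = mean(E)/365.

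- E uniform on 0-45: 22.5/365 = 6.2%.
- E = 45 for everyone: 45/365 = 12.3%. This is an upper-end case, since many would enrol sooner.

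If 20% to 50% of 500 patients are operated on (assumed), 100 to 250 have surgery. The gap then holds 100 × 0.062 = 6 to 250 × 0.062 = 15 patients in the first case, and 100 × 0.123 = 12 to 250 × 0.123 = 31 in the second.

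The result depends on how early surgery happens. If nobody is operated on within 45 days of clinic, the share is 0% for patients enrolled inside the window. If time to surgery is exponential with rate λ = ln 2/median, truncated at 365 days, and E is uniform on 0-45, the share is [1 − (1 − e^(−45λ))/(45λ)] / (1 − e^(−365λ)). This gives about 11%, 16% and 22% for medians of 180, 90 and 60 days. That shape puts the highest operation rate on the day of clinic, so it is only a sensitivity check.

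**5. Which outcomes are affected.** For HRQoL only the first 45 days matter, because later enrolees contribute no patient-reported data (Section 9.2). For record-based complications and re-operations the gap has no upper limit; enrolment at day 90 with evenly spread surgery would give 90/365 = 24.7%, for late enrolees only.

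**The case against.** The strongest reply is that one phrase is being set against a consistent definition elsewhere. The objectives, Section 7, Section 9.5.1 and the next sentence of Section 9.7 describe the surgical group without any enrolment limit, and the Lay Summary says "Afterwards data are collected from all patients undergoing decompressive surgery, other surgery or being treated conservatively for CM1 in participating UK neurosurgical units". The protocol is also loose with its anchors: the Section 9 table places recruitment at baseline, and the Synopsis runs follow-up from recruitment. Enrolment in Section 9.7 may simply mean baseline. This stands to the extent that the text is an inconsistency and not a fixed exclusion rule. It does not remove the need for correction, because Section 9.7 is the only operational instruction for finding these patients and its wording is narrower than the objectives.

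A reader might infer that missed patients necessarily fall into the natural-history group and contaminate objective 3 by a calculable percentage. The documents do not support that. The group is defined by treatment (no decompression in Section 6, no surgery for CM1 in the Synopsis), not as whatever remains after the surgical search. Patient B meets neither definition. Misplacement is a risk of poor classification and not a consequence of the stated rule.

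A reader might also infer that Section 9.7 removes these patients whatever else holds. It does so only if Section 8.3 is judged at first clinic. Appendix B points that way but does not settle it.

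Finally, it is fair to object that dating Section 8.3 at first clinic is more than a wording change. It would admit people who consent after their operation, and patients who died or lost capacity afterwards could be under-represented, which could bias complication rates downwards. That stands, and the choice belongs to the sponsor.

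**Conclusion.** The point holds as a conflict of time origin. Section 9.7 searches from enrolment, follow-up and eligibility identification start at first clinic, and the objectives set no enrolment limit. Together with the undated exclusion in Section 8.3, this leaves patients decompressed between clinic and enrolment either liable to be missed or barred, with no statement of which.

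The size is unknown. The range of about 6% to 12% of first-year operations rests on evenly spread surgery and on enrolment within 45 days, and the true share could be close to nil or higher. The inconsistency needs correcting at any size, because whoever is lost is selected by having early surgery.

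**What to change.** 1. In Section 9.7, count decompression from the first neurosurgical clinic instead of from enrolment. This matches the objectives and the follow-up clock. It costs one wording change by amendment and a database check of surgery date against clinic date, with no extra patients or visits.
2. In Sections 9.6 and 11.2, state that a questionnaire completed after decompression is not used as the baseline score in the change analysis. Such patients can still contribute to complication and re-operation rates and, where they were enrolled within the 45-day window, to the post-operative comparison with UK norms. The cost is a few missing change scores.
3. The sponsor should reconcile Section 8.3 with Section 9.2 and Appendix B by stating the date at which prior intervention is judged. This is a design choice and is left open here. If patients who consent after surgery are admitted, report complication and re-operation rates with and without them, since consent after surgery can itself select patients.
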